
For non-clinical questions (i.e., unrelated to patient eligibility, treatment, or clinical data submission) contact the CTSU Help Desk by phone or e-mail:
 
CTSU General Information Line – [name], or [contact]. All calls and correspondence will be triaged to the appropriate CTSU representative.
		

The CTSU Web site is located at https://www.ctsuo.org
		

Rev. 6/14, 2/15,  
1/16

Schema

Accrual: 515

1. Resectable oropharynx carcinoma, p16+ by IHC, PS 0-1
2. Credentialing of surgeon required as part of site participation, neck levels dissected and nodal yield (> nodes/neck)
3. Radiotherapy will be given with an intensity modulated radiotherapy (IMRT) technique. Standard ECOG credentialing through QARC will be required.
4. Stratify by current/former smoking history(≤ 10pk-yr vs. > 10pk-yr)
5. Low Risk: T1-T2, N0-N1 AND clear (≥ 3mm) margins, AND no ECE or PNI/LVI.
6. High Risk: Any of the following features: one or more positive margin(s) with any T stage, OR "Extensive" (> 1mm) ECE, OR ≥ 5 metastatic lymph nodes (regardless of primary tumor margin status).
7. Intermediate Risk: Any of the following features: one or more "close" (< 3mm) margin(s), OR "Minimal" (≤ 1mm) ECE, OR N2a (1 or more lymph node >3cm in diameter), OR N2b (2-4 lymph nodes positive, any diameter ≤ 6cm), OR with perineural invasion or lymphovascular invasion.
8. If = 2 events are observed among the first ten patients registered on Arm A within one year, currently enrolled and subsequently enrolled low risk patients who have not progressed will be treated with IMRT 50 Gy
9. Patients found to have N2c (bilateral nodes), OR N3 (>6cm node) disease on final pathologic analysis.

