3.2 Registration/Randomization to Step 2 - Arms A, B, C, and D

Rev. 6/14

- \_\_\_\_\_ 3.2.1 Histopathologic assessment of surgical pathology must include examination for perineural invasion (PNI) and lymphovascular invasion (LVI) and reported as absent or present. The absence or presence of extracapsular extension (ECE) requires gross and microscopic assessment and is defined to be:
- absent (negative or nodal metastasis with smooth/rounded leading edge confined to thickened capsule/pseudocapsule),
  - present - minimal (tumor extends  $\leq$  1 mm beyond the lymph node capsule), or
  - present - extensive (Gross, tumor extends  $>$ 1 mm beyond the lymph node capsule (includes soft tissue metastasis)

Rev. 2/15  
Rev. 1/16

- \_\_\_\_\_ 3.2.2 Patient must be stratified/classified into one of the following risk categories:
- The highest risk feature assessed pathologically will determine the patient's category/treatment arm assignment.
- Low Risk: T1-T2, N0-N1 AND clear ( $\geq$  3mm) margins, AND no ECE or PNI/LVI.
  - High Risk: Any of the following features: one or more positive margin(s) with any T stage, OR "Extensive" ( $>$  1mm) ECE, OR  $\geq$  5 metastatic lymph nodes (regardless of primary tumor margin status).
  - Intermediate Risk: Any of the following features: one or more "close" ( $<$  3mm) margin(s), OR "Minimal" ( $\leq$  1mm) ECE, OR N2a (1 or more lymph node  $>$  3cm in diameter), OR N2b (2-4 lymph nodes positive, any diameter  $\leq$  6cm), OR with perineural invasion or lymphovascular invasion.
  - Unknown Risk: Patients found to have N2C or N3 disease on final pathologic analysis are at unknown risk for recurrence, but are not candidates for deintensified adjuvant therapy in this trial. These patients will be treated on Arm C.
  - **Patients not categorized into the appropriate risk category will be considered ineligible for the study.**

Rev. 1/16

Rev. 2/15  
Rev. 9/16

- \_\_\_\_\_ 3.2.3 Patient must be registered/randomized to Step 2 within a maximum of 7 weeks following surgery.
- \_\_\_\_\_ 3.2.4 Women of childbearing potential and sexually active males are strongly advised to use an accepted and effective method of contraception

\_\_\_\_\_  
Physician Signature

\_\_\_\_\_  
Date

**OPTIONAL:** This signature line is provided for use by institutions wishing to use the eligibility checklist as source documentation.

Rev. Add8

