4.2.4 Stratification and Classification Factors

4.2.4.1 Classification Factors

- The highest risk feature assessed pathologically will determine the patient's category/treatment arm assignment.
  - Low Risk: T1-T2, N0-N1, with clear ( $\geq 3$ mm) margins, and without any ECE or PNI/LVI.
  - High Risk: Any T stage with positive margin(s), meaning tumor at the specimen edge, not superceded by an additional, tumor free margin, OR "Extensive" ( $> 1$ mm) ECE, OR  $\geq 5$  metastatic

Rev. 7/13

Rev. 2/15

Rev. 6/14

Rev. 1/16

lymph nodes, regardless of primary tumor margin status.

- Intermediate Risk: Any T stage with one or more “close” (<3mm) margin(s) OR “Minimal” (≤ 1mm) ECE, OR 1 or more lymph node >3cm in diameter (N2a neck disease), OR 2-4 lymph nodes positive, any diameter ≤ 6cm (N2b neck disease (regardless of primary tumor margin status)], OR with perineural invasion or lymphovascular invasion.
- Unknown Risk: Pathologic N2c (bilateral nodes), OR Pathologic N3 (> 6cm node)

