#### 5.1.1 Surgical Credentialing/Quality Control

Rev. 2/14

Surgeons must be credentialed prior to enrolling patients on the trial. Adequate experience in at least one of the three categories of transoral surgery (TLM, TORS and non-laser/non-robotic transoral resections) must be demonstrated to ensure quality control. Only transoral oropharynx cancer resections are applicable; oral cavity and larynx surgeries are not applicable, even if transoral in approach. For each category of transoral surgery this experience will be confirmed, as follows:

Rev. 1/16

- Each participating surgeon must document that he/she has performed a minimum number of 20 cases of transoral excision for OPSCC as the primary surgeon;
- Each participating surgeon must document that he/she has performed at least 10 transoral resections of OPC in the past 12 months;
- The Principal Investigator will review each surgeon's submitted pathology report and operative notes for 10 OPSCC cases excised using a modality specific technique for which credentialing is being sought;
- Responses to a surgeon questionnaire;

Surgical technique (for both TLM and TORS) will be standardized. Transoral resection of the oropharyngeal tumor will be performed at the discretion of the attending head and neck surgeon. The type of resection chosen should provide complete removal of the primary lesion with negative gross margins; this is not subject to quality assurance review; documentation of margins by frozen section at surgery is required. For en bloc resections, the gross margins will be assessed by palpation. If it is clear that a margin is close or positive -

the specimen will be inked and frozen section margins will be taken from the surgical specimen. 3- 5 mm of mobile soft tissue, then the surgeon will do a wide re-resection of that margin. The specimens will then be inked by the surgeon, avoiding ink on the main specimen in areas of a close or positive margin (which has undergone re-resection) will be done by the surgeon. Standard terminology will rely on a deep margin and four quadrants: anterior, posterior, medial, lateral. However, specific issues and approaches should vary by subsite, as detailed below.

Rev. 2/14

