Surgery should be performed within 3 weeks after registration onto the study and not more than 4 weeks after study registration. If more than one surgery is performed as part of the Arm S resection, all surgeries must be completed within 4 weeks of registration to Arm S. Reconstruction of surgical defects should be performed using conventional techniques at the discretion of the surgeon, most often with primary closure or healing by secondary intention. In general, patients with T1 and T2 OPC do not require microvascular reconstruction flaps, therefore patients requiring free flaps will be replaced with another patient and listed as a minor protocol deviation. Secondary intention healing is recommended when appropriate but should not be pursued at the expense of obtaining wide, tumor-free margins. Reconstructive closure with local flaps is at the discretion of the surgeon.

Rev.1/16

For tonsillar carcinoma, the extent of en bloc-resection must include a tongue base margin, soft palate margin, complete constrictor margin, a complete anterior tonsillar pillar margin and a complete posterior tonsillar pillar margin. ). Simple “tonsillectomy” should not be performed.. The surgeon should aim to achieve resection of tumor and surrounding structures, with an attempt made to achieve a 1 cm gross visual mucosal margin, with a minimum of 3 mm microscopic margins. For tonsillar fossa cancers, the exception to this will be the superior constrictor, which represents the deep margin which will necessarily obviate a stipulated microscopic margin but must be histologically negative . However, the constrictor margin must have a gross margin of 5 mm of mobile tissue. Therefore, given the three-dimensional complexity of the superior constrictor, margin status will be assessed as a binary endpoint: as clear or positive. These stipulations are subject to quality assurance review.

For tongue-base carcinoma, a standard en bloc resection is preferred to include, wide mucosal margins, resection of the underlying muscle, as well as the inferior portions of the tonsillar pillars (anterior and posterior). The surgeon should aim to achieve an en-bloc resection of tumor and surrounding structures, with an attempt made to achieve a minimum of 1 cm gross visual margins with  $\geq 3$ mm microscopic margins. These are recommendations subject to quality assurance review.

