5.1.3.3

For tongue-base carcinoma, a standard en bloc resection is preferred to include resection of the underlying superior constrictor muscle, as well as the tonsillar pillars (anterior and posterior) and cranial and caudal margins. The surgeon should aim to achieve an en-bloc resection of tumor and surrounding structures, with an attempt made to achieve a minimum of 1 cm gross visual margins with 3 mm microscopic margins. These are recommendations subject to quality assurance review. The tongue base musculature represents the deep margin, to be sent separately for margin analysis.

Rev.1/16

5.1.3.4

For hybrid lesions, the same principles of four-quadrant margin assessment will apply, with appropriate deep margin constituting the base of tongue and/or constrictor parapharyngeal fat as the deep margin.

Rev.1/16

5.1.3.5

A positive margin is defined as carcinoma in situ or invasive carcinoma at the margin of resection, which is not superceded by additional tissue (a new separate margin) found to be histopathologically free of disease. If a new separate margin is obtained adjacent to a specimen or margin containing CIS or invasive SCC is deemed pathologically negative, the patient will be considered to have “close” margins.

5.1.4

Margin excision and histopathologic assessment.

Intraoperatively, the surgeon must send 4 quadrant margins plus deep margin (recommend 3 mm diameter at minimum), submitting the oriented specimen to the pathologist. A positive margin found on final pathologic analysis after negative frozen sections will be classified as a “close” negative margin resection (R0) and entered in the RT randomization (Arms B-C) if additional histopathologically benign tissue surrounding and deep to the region of concern is removed and analyzed pathologically.

Recommendation for standard practice (permanent section histopathology). It is recommended to perform photodocumentation of the specimen by the pathologist after these procedures, using high resolution digital photography with annotation. If the surgeon obtains additional margins from the patient, the “new margins” should refer back to the geometric orientation of the resected tumor specimen. A statement by the pathologist in the final surgical pathology report should point out that this “new” margin represents the final margin of resection in addition to its histologic status.

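### The rule that a positive margin re-resected to negative counts as close (Arms B/C) is stated in 5.1.3.5 but missing from the arm-assigning text, so a literal checklist reading could put an otherwise low-risk patient in Arm A

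*Combined protocol and SAP*

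**What the plan says.** **The specific rule.** Section 5.1.3.5 does not call a margin positive once it has been superseded by new tissue free of disease. If the new margin next to tissue containing carcinoma in situ or invasive carcinoma "is deemed pathologically negative, the patient will be considered to have “close” margins". No distance is mentioned. Section 5.1.4 takes a related case, a margin positive on final pathology after negative frozen sections. It classes that case as a close "negative margin resection (R0) and entered in the RT randomization (Arms B-C) if additional histopathologically benign tissue" around and beneath the area has been removed and examined.

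**The arm-assigning text.** Schema note 5 reads "Low Risk: T1-T2, N0-N1 AND clear (≥ 3mm) margins, AND no ECE or PNI/LVI". Sections 3.2.2, 4.2.4.1 and 5.1.8.1 use the same cut-off, with close meaning under 3 mm. Sections 5.1.4.3 and 5.1.4.4 also define clear and close by distance, and 5.1.4.3 treats a new margin as the final one. Section 4.2.4.1 limits high risk to "Any T stage with positive margin(s), meaning tumor at the specimen edge, not superceded by an additional, tumor free margin", but does not say which category a superseded margin then falls into.

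**Related rules.** Section 3.2.2 states "The highest risk feature assessed pathologically will determine the patient's category/treatment arm assignment" and "Patients not categorized into the appropriate risk category will be considered ineligible for the study". The opening of Section 9 says that risk status is defined in Section 5.1. For a margin that is clearly close or positive at surgery, 5.1.1 says "then the surgeon will do a wide re-resection of that margin". For the superior constrictor deep margin of tonsillar fossa cancers, 5.1.1 says "margin status will be assessed as a binary endpoint: as clear or positive".

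**The concern.** The protocol's own technique creates the situation: a positive margin is to be re-resected, and the new margin may well be negative by 3 mm or more. If the patient has no other risk feature, the arm then depends on whether the site applies 5.1.3.5 or only the distance cut-off in the checklist. The first gives postoperative radiotherapy and the second gives observation.

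What is at stake is mainly the treatment of that individual patient. There is a secondary effect on the analyses. A wrongly categorised patient is ineligible under 3.2.2, and so should leave both the Arm A interim look (first 10 eligible and treated patients, Section 9.3) and the risk-distribution estimate (eligible patients on Step 2, Section 9.4). A case that nobody notices stays in both.

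**Working it through.** The main check is a comparison of texts. Take one test patient: pT1-2, N0-1, no extracapsular extension, perineural or lymphovascular invasion; the initial margin contained tumour; the new separate margin is negative.

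| Text applied | New margin ≥ 3 mm | New margin < 3 mm |
|---|---|---|
| 5.1.3.5 (and 5.1.4 where it applies) | close: Arms B/C | close: Arms B/C |
| Schema, 3.2.2, 4.2.4.1, 5.1.8.1, read literally with 5.1.4.3/5.1.4.4 | clear: Arm A | close: Arms B/C |

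The readings part only in the first column, and only for a patient with no other intermediate- or high-risk feature. One site needs separate mention. Because 5.1.1 scores the superior constrictor margin only as clear or positive, a re-resected negative margin there could be scored clear at any distance, while 5.1.3.5 would make the patient close.

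**Number affected.** The documents give no re-resection rate and no split of re-resected margins at 3 mm, so no count can be derived. The group it would come from is small: 8% of 104 evaluable patients at the interim analysis were low risk (0.08 × 104 = 8.3). Section 9.3 expects about 30 low-risk patients in one place and 38 in another.

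**Chance of detection.** Surgical quality assurance reads operative and surgical pathology reports (5.1.6.1), and the pathologist is asked to identify a new final margin (5.1.4.3). Against that, the reporting categories in 11.2.1 and Appendix I are distance-based, so such a margin is reported as negative, and the central review list in 12.1 does not include margins.

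**Arm A interim rule, illustration only.** The rule triggers at 2 or more failures in 10. With all ten patients at failure risk p = 0.10, P(≥ 2) = 0.2639. This reproduces the 0.26 in the table in 9.3, reading its 0.10 column as a failure probability. With nine patients at p and one misplaced patient at q, the rise is (q − p) × P(exactly 1 failure in 9).

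- P(exactly 1 in 9) = 9 × 0.05 × 0.95⁸ = 0.2985 at p = 0.05, and 9 × 0.10 × 0.90⁸ = 0.3874 at p = 0.10.
- p = 0.05, q = 0.20: 0.0861 + 0.15 × 0.2985 = 0.131.
- p = 0.10, q = 0.20: 0.2639 + 0.10 × 0.3874 = 0.303.
- Over q from 0.10 to 0.30, the rise is 1.5 to 7.5 points at p = 0.05 and 0 to 7.7 points at p = 0.10.

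The values of q, and p = 0.05, are assumptions; the documents give no failure risk for such a patient. If the case is detected and excluded, the misplaced patient contributes nothing.

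**The case against.** The strongest reply is that the protocol already answers the question. The arm-assigning sections do not discuss re-resected margins. Section 5.1.8.1 requires that close margins be absent, 5.1.3.5 says this patient has close margins, and Section 9 points to Section 5.1 for risk status. Together with the highest-risk-feature rule, this gives Arms B/C. The operating surgeon has to follow 5.1.3 and 5.1.4 in any case, and 5.1.8.2 and 5.1.8.3 tell sites to ask when in doubt. Moreover, 5.1.4.3 gives no method for a combined distance when the new margin is a separate piece, so even the literal result of clear is an inference.

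Most of this stands. A reader might infer that the checklist expressly classes the re-resected margin as clear, so that the protocol contradicts itself. It does not: it is silent, and the specific rule governs. What survives is narrower. The eligibility checklist and registration text are what a site uses to assign the arm, they state a complete-looking distance rule, and that rule applied as written gives the wrong arm for this patient. Section 5.1.8.1 does not settle it alone, because it too ties close to under 3 mm.

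It can also be said that accrual was projected to end in February 2017 and that Appendix X describes classification in the past tense. If enrolment is over, the wording changes have little practical value and only the check of existing reports matters.

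**Conclusion.** The point holds as a minor one: a stated rule is not carried into the text that assigns the arm. It affects an otherwise low-risk patient whose tumour-bearing margin was re-resected to a negative margin of at least 3 mm, at a site that relies on the checklist alone. The number is unknown and probably very small. No sample size, power or error rate changes.

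Four stronger readings are not supported:

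- **Arm D as a possible destination.** The Schema and 3.2.2 omit the supersession qualifier, but 4.2.4.1, 5.1.3.5, 5.1.8.2, 11.2.1 and Appendix I all exclude superseded margins from positive.
- **Bias between Arms B and C.** The risk class is fixed before randomisation, so a misplaced patient is missing from the randomised group as a whole.
- **The 13 of 104 patients flagged as potentially misclassified (Section 9.3).** The cause is not given, so they cannot be attributed to this rule.
- **A material effect on the Arm A rule.** The shift of about 4 points needs an undetected case among the first 10 patients and an assumed 20% failure risk. The range considered includes zero, and any increase makes the switch to 50 Gy more likely, which is the cautious direction.

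**What to change.** 1. Add to 3.2.2, the Schema, 4.2.4.1, 5.1.4.3/5.1.4.4 and 5.1.8.1: *a margin or specimen that contained CIS or invasive carcinoma and was superseded by a new separate negative margin counts as close (intermediate risk, Arms B/C) whatever the distance, per 5.1.3.5; a margin that was only close and tumour-negative before re-resection is classed by its final distance.* The second clause is needed. Section 5.1.1 also calls for re-resection of margins that are merely close, and a blanket rule for all re-resected margins would send some low-risk patients to radiotherapy that 5.1.3.5 does not require.
2. State whether this applies to the superior constrictor deep margin, which 5.1.1 scores only as clear or positive.
3. Add the supersession qualifier from 4.2.4.1 to the high-risk line in 3.2.2 and the Schema.
4. If accrual is complete, check the Arm A operative and pathology reports for such patients within the existing surgical quality assurance. Apply the 3.2.2 eligibility rule before the Arm A and risk-distribution analyses.

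The cost is a few lines of amendment text and a review of reports already collected for about 30 to 38 patients. No new patients, visits or forms are needed.

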#### 5.1.5 Neck Dissection

- 5.1.5.1 A formal selective or modified radical neck dissection, level II-IV, will be performed in all cases. Numbering and/or nomenclature outlined in the “Neck Dissection Guide” will be used. Resection of levels II-IV are required, with levels I and/or V electively dissected at the discretion of the attending surgeon. The neck dissection should be oriented or separately partitioned in order to identify levels of lymph nodes encompassed in the dissection.

Rev.1/16

- 5.1.5.2 Extent of neck dissection  
Patients will undergo ipsilateral selective or modified radical neck dissection of levels II-IV for lateralized lesions of the tongue-base, tonsillar region and/or glossopharyngeal sulcus. Midline lesions are discouraged from accrual to this trial. For patients with SCC of the base of tongue that approaches within 1 cm of the midline, a contralateral neck dissection should be performed, also of levels II-IV. For ipsilateral and contralateral lymphadenectomy, level I-b and V may be electively dissected at the discretion of the attending surgeon, but is not required.
- 5.1.5.3 A minimum of 20 lymph nodes per dissected side of the neck is required and is subject to quality assurance review. Removal of  $< 20$  but  $> 15$  lymph nodes will be considered a minor protocol deviation and recorded.
- 5.1.5.4 For patients with SCC of the base of tongue where the tumor is within 1 cm of the midline, a contralateral neck dissection should be performed, also of levels II-IV. For

ipsilateral and contralateral lymphadenectomy, level I and/or V may be electively dissected at the discretion of the attending surgeon, but is not required. For lateralized base of tongue cancers not within 1 cm of midline, the contralateral neck treatment is at the discretion of the treating surgeon. The neck dissection should be oriented or separately partitioned in order to identify levels of lymph nodes encompassed in the neck dissection specimen.

5.1.5.5 Adequacy of Nodal Harvest: Histopathologic assessment of 20 nodes is required for all neck dissection specimens. Realizing that there is some anatomic variation from patient to patient, an absolute minimum of 15 nodes is required. More specifically, specimens of < 20 but > 15 lymph nodes would be an acceptable protocol violation.

5.1.5.6 Pathologic assessment of extracapsular extension (ECE): Lymph nodes  $\leq$  2 cm in greatest dimension are considered adequately assessed with one section. Multiple lymph nodes  $\leq$  2 cm in greatest dimension may be submitted in a single cassette. Lymph nodes > 2 cm in greatest dimension require multiple sections (and possibly multiple cassettes); specifically, one section per 1 cm should be submitted. Sections should include the edge of the lymph node that interfaces with surrounding fibroadipose tissue.

5.1.5.7 Ligation of arterial blood supply of the primary oropharyngeal tumor is required to avoid major postoperative pharyngeal hemorrhage.

- At a minimum, it is recommended that the surgeon ligate the ipsilateral lingual and facial arteries. At the surgeon's discretion and judgment, ligation of other arteries, such as the ascending pharyngeal and superior thyroid, may be considered.
- If the external carotid arterial trunk itself is ligated, the surgeon must ligate the vessel at an adequate distance from the carotid bulb to avoid injury to the internal carotid artery. Care should be taken to avoid injuring the internal carotid artery if ligating the ascending pharyngeal artery, since its takeoff may occur posteriorly putting the ICA at risk.
- The attending surgeon is directed to perform this portion of the procedure him/herself.
- The arteries should be ligated but not divided.
- The case report form will now require the documentation, taken from the operative report, confirming that arterial ligation was performed and delineating which vessels were ligated.
- Please contact the study chair, [name], with any questions or to clarify.

Rev. 6/14

Rev. 1/16  
Rev. 9/16  
Rev. Add8

Failure to perform arterial ligation, and provide written documentation of this critical aspect of the surgery, will constitute a reportable deviation which will be forwarded to the Credentialing Committee and subject to peer-review and appropriate action. Such action may include suspension of the surgeon's credentials for involvement in the trial, thus preventing further accrual to the trial.

